2.5 Definitions

Day 1: The day when subject starts antibiotic treatment. The start of SCOUT-directed treatment is on Day 6, after five days of initial antibiotic treatment.

Fever/Febrile: A documented temperature of at least 100.4° F or 38° C, measured anywhere on the body (oral, axillary, tympanic, or rectal).

Afebrile: NO documented temperature greater than or equal to 100.4 °F or 38°C, measured anywhere on the body (oral, axillary, tympanic, or rectal) in the 24 hours prior to the enrollment visit.

Treatment failure: A subject will be categorized as a treatment failure, if he/she has a symptomatic UTI in period between Day 6 through the Day 11 – 14 Test of Cure (TOC) Visit:

I. The presence of at least one of the symptoms consistent with the diagnosis of UTI including:

- Symptoms for all children (ages two months to 10 years):
 - fever (a documented temperature of at least 100.4 °F OR 38°C measured anywhere on the body)
 - dysuria
- Additional symptoms for children > 2 years of age:
 - suprapubic, abdominal, or flank pain or tenderness OR
 - urinary urgency, frequency, or hesitancy (defined as an increase in these symptoms from pre-diagnosis conditions)
- Additional symptoms for children ≥ 2 months to 2 years of age:
 - poor feeding OR
 - vomiting

AND

II. Pyuria on urinalysis

- ≥ 10 WBC/mm³ (uncentrifuged specimen) OR
- ≥ 5 WBC/hpf (centrifuged specimen), OR
- Leukocyte esterase \geq trace on dipstick.

AND

III. Culture proven infection with a single uropathogen:

- $\geq 5 \times 10^4$ CFU/mL (catheterized or suprapubic aspiration urine specimen) OR
- $\geq 10^5$ CFU/mL (clean void specimen).

NOTE: As per the above criteria, asymptomatic subjects (including subjects assessed as having asymptomatic bacteriuria) at the Day 11-14 TOC visit will NOT be considered a treatment failure for the primary outcome measure.

Recurrent Infection: A UTI that occurs anytime after the Day 11 – 14 Test of Cure Visit. This can include a relapse infection or reinfection.

Asymptomatic Bacteriuria: Asymptomatic Bacteriuria is defined in any SCOUT subject by:

(1) Absence of symptoms attributable to UTI including fever AND/OR the following:

- Symptoms for all children (ages two months to 10 years):
 - fever (a documented temperature of at least 100.4 °F OR 38°C measured anywhere on the body)
 - dysuria
- Additional symptoms for children > 2 years of age:
 - suprapubic, abdominal, or flank pain or tenderness OR
 - urinary urgency, frequency, or hesitancy (defined as an increase in these symptoms from pre-diagnosis conditions)
- Additional symptoms for children ≥ 2 months to 2 years of age:
 - poor feeding OR
 - vomiting

AND

(2) A positive urine culture

- 5×10^4 CFU/mL (catheterized or suprapubic aspiration urine specimen) OR
- $\geq 10^5$ CFU/mL (clean void specimen).

Antibiotic Resistance: Resistance against amoxicillin-clavulanate, TMP-SMX or evidence of ESBL production.

Multiple Drug Antibiotic Resistance: Resistance to two or more agents (this includes resistance against amoxicillin and amoxicillin-clavulanate).

***K. pneumoniae* Multiple Drug Antibiotic Resistance:** Resistance to either two or more of the three agents (TMP-SMX, amoxicillin-clavulanate, cefixime, or cephalexin) that the SCOUT Study will test (excluding amoxicillin resistance).

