A subject will be categorized as a treatment failure, if he/she has a symptomatic UTI in period between Day 6 through the Day 11 – 14 Test of Cure (TOC) Visit: (See Appendix B)

- Symptoms for all children (ages two months to 10 years):
 - fever (a documented temperature of at least 100.4 °F OR 38°C measured anywhere on the body)
 - dysuria
- Additional symptoms for children > 2 years of age:
 - suprapubic, abdominal, or flank pain or tenderness OR
 - urinary urgency, frequency, or hesitancy (defined as an increase in these symptoms from pre-diagnosis conditions)
- Additional symptoms for children ≥ 2 months to 2 years of age:
 - poor feeding OR
 - vomiting

AND

I. Pyuria on urinalysis

- ≥ 10 WBC/mm³ (uncentrifuged specimen) OR
 - ≥ 5 WBC/hpf (centrifuged specimen), OR
- Leukocyte esterase \geq trace on dipstick.

AND

II. Culture proven infection with a single uropathogen:

- $\geq 5 \times 10^4$ CFU/mL (catheterized or suprapubic aspiration urine specimen) OR
- $\geq 10^5$ CFU/mL (clean void specimen).

NOTE: As per the above criteria, asymptomatic subjects (including subjects assessed as having asymptomatic bacteriuria) at the Day 11-14 TOC visit will NOT be considered a treatment failure for the primary outcome measure.

Pyuria on urinalysis:

- ≥ 10 WBC/mm³ (uncentrifuged specimen) OR
- ≥ 5 WBC/hpf (centrifuged specimen), OR
- Leukocyte esterase \geq trace on dipstick.

Recurrent Infection: A UTI that occurs anytime after the Day 11 – 14 Test of Cure Visit. This can include a relapse infection or reinfection. (See Appendix B)

Asymptomatic Bacteriuria:

Asymptomatic Bacteriuria is defined in any SCOUT subject by:

(1) Absence of symptoms attributable to UTI including fever AND/OR the following:

- Symptoms for all children (ages two months to 10 years):
 - fever (a documented temperature of at least 100.4 °F OR 38°C measured anywhere on the body)
 - dysuria
- Additional symptoms for children > 2 years of age:
 - suprapubic, abdominal, or flank pain or tenderness OR
 - urinary urgency, frequency, or hesitancy (defined as an increase in these symptoms from pre-diagnosis conditions)
- Additional symptoms for children \geq 2 months to 2 years of age:
 - poor feeding OR
 - vomiting

AND

(2) A positive urine culture with a single uropathogen:

- $\geq 5 \times 10^4$ CFU/mL (catheterized or suprapubic aspiration urine specimen) OR
- $>10^5$ CFU/mL (clean void specimen).

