- Comparison of overall fraction of gut microbiome community represented by gammaproteobacteria measured by culture-independent marker gene sequencing at each follow-up visit following short-course and standard-course antibiotic exposure.
- Comparison of average ecological similarity between microbial communities within and between treatment groups at each follow-up following short-course and standard-course antibiotic exposure.

Spectrum of Stool Bacteria

- Description of the bacteria present on the aerobic stool cultures obtained at each the three study time points.

Table 2: SCOUT Study Possible Outcomes Day 6-44.

Outcome scenario	UTI Symptomology		Urine collection method	Urine culture result		Pyuria present		Composite Outcome/Follow-up	Repeat urine culture result/outcome	
	Symp	Asymp ¹		+	-	Yes	NO			
1	X		Clean Catch or Catheter	X		X		Treatment Failure		
2	X		Clean Catch or Catheter	X			X	No UTI		
3	X		Clean Catch or Catheter		X	X		Follow-up required. Contact subject in 24-48 hrs. Perform repeat urine culture if still symptomatic.	+	-
4	X		Clean Catch or Catheter		X		X	Follow-up required. Contact subject in 24-48 hrs - Perform repeat urine culture if still symptomatic.	+	-
5a		X	Clean Catch	X		X		No UTI (Asymptomatic Bacteriuria)		
5b		X	Bag	X		X		No UTI (Asymptomatic Bacteriuria)		
6a		X	Clean Catch	X			X	No UTI (Asymptomatic Bacteriuria)		
6b		X	Bag	X			X	No UTI (Asymptomatic Bacteriuria)		

7		X	Clean Catch or Bag		X	X		No UTI		
8		X	Clean Catch or Bag		X		X	No UTI		

¹ If a urine sample cannot be obtained from asymptomatic subjects at the TOC visit, another attempt will be made to obtain a sample at the Day 24-30 Outcome Assessment Visit. These subjects are evaluable for the primary endpoint measure (considered a success); however, they will not be evaluable for the asymptomatic bacteriuria or urine culture secondary endpoints.

[figure not shown]
Note: Urine collection in children that are toilet trained will be by clean catch. For infants and young children (prior to being toilet trained) the initial urine sample will be obtained by bag method (if asymptomatic), clean-catch if symptomatic (or catheterization if a sample cannot be obtained by clean-catch). Also see Section 9.2.3.1 for listing of urine collection by age group/symptomology.

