The site's microbiology and hematology labs will run tests on the urine as per standard CHOP and PITT procedures for a urine culture and urinalysis. These standards include the following differences in procedures:

- Cultures will be checked for growth after
 - CHOP: 20-24 hours.
 - PITT: at least 18 hours.
- Cultures are reported as “No growth” if
 - CHOP: $< 10^2$ CFU/ml
 - PITT: there is no growth
- Cultures will be inoculated with:
 - CHOP: blue (10µl) loops or green (1µl) loops
 - PITT: green (1µl) loops only
- Individual colony counts will be reported for
 - CHOP: up to 3 organisms
 - PITT: up to 2 organisms:
 - If the two organisms are between $10^4 - 10^5$ CFU/ml, ID and sensitivities are performed on each of them
 - If one is $>10^4$ CFU/ml and one is $<10^4$ CFU/ml, ID and sensitivities performed on the former and the latter is only described

Routine Evaluations

When clinically appropriate, routine laboratory measurements will also be performed according to the medical judgment of the investigators.

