2.2.4 Secondary outcomes

The secondary outcome measures are:

- a. Recurrent infection (includes a relapse UTI or a reinfection) at any time after the TOC visit (Day 11-14)
- b. Asymptomatic bacteriuria at the TOC visit
- c. Colonization with antimicrobial resistant E.coli and K. pneumoniae in the gastrointestinal tract as assessed through Day 24-30.
- d. Presentation of clinical symptoms that may be related to UTI prior to or at the TOC visit
- e. Positive urine culture prior to or at the TOC visit

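### The SAP definition of asymptomatic bacteriuria omits the protocol's single-uropathogen condition, so the two documents can classify the same child differently on secondary endpoint b

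*SAP*

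**What the plan says.** Protocol section 3 defines asymptomatic bacteriuria as no UTI symptoms together with "A positive urine culture with a single uropathogen" at stated colony counts for catheter or suprapubic specimens and for clean-void specimens. SAP section 2.5 repeats the symptom part, but its culture part reads "2) A positive urine culture", followed by colony counts for the same specimen types. It does not mention the number of organisms.

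In the treatment-failure definition of the same SAP section, the condition is kept: "Culture proven infection with a single uropathogen".

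SAP section 2.2.4 lists "Asymptomatic bacteriuria at the TOC visit" as secondary endpoint b and, separately, "Positive urine culture prior to or at the TOC visit" as endpoint e. SAP section 4.2.3 compares both between arms through a two-sided 95% confidence limit for the difference in proportions.

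Protocol section 9.2.1 describes the urine laboratories: "Individual colony counts will be reported for" up to three organisms at CHOP and up to two at PITT. Protocol section 8.3 and Table 6 have asymptomatic children who are not toilet trained give bag specimens, and rows 5b and 6b of protocol Table 2 score a positive bag culture as asymptomatic bacteriuria.

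**The concern.** The SAP is the document from which the analysis tables are produced, and it states the organism rule for one outcome but not for the other in the same section. Someone applying it could reasonably conclude that the rule is meant for treatment failure only. Children with two organisms in the urine at the test-of-cure visit could then be events for endpoint b, although the protocol's own definition excludes them.

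The stake lies in how a null result will be used. Protocol section 12.4 expects no difference in asymptomatic bacteriuria, symptoms and urine culture, and says it will read such a result as showing that the short course is not inferior in clearing bacteria from the urinary tract. Under that reading, the rule for what counts as an event affects the conclusion. It should not be left open until the data are unblinded.

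**Working it through.** **1. The definitions side by side.**

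| Outcome | Protocol section 3 | SAP section 2.5 |
|---|---|---|
| Treatment failure (primary) | single uropathogen required | single uropathogen required |
| Asymptomatic bacteriuria (endpoint b) | single uropathogen required | number of organisms not stated |
| Positive urine culture (endpoint e) | no definition of its own | no definition of its own |

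The contradiction is confined to the middle row. In the last row both documents are silent; SAP section 4.2.3 says only that all treatment failures count as positive for endpoint e.

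**2. Can such cultures arise?** Yes. Both laboratories report more than one organism per culture, and bag specimens are used in part of the population. Neither document says how often this occurs or how a multi-organism follow-up culture is to be classified.

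**3. The plan's own figure.** SAP section 3.2 gives 326 per arm for the primary endpoint, from failure rates of 5% in both arms, a margin of 5 points, one-sided alpha 0.05 and 90% power:

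n = (1.645 + 1.282)² × (0.05×0.95 + 0.05×0.95) / 0.05² = 8.564 × 38 = 325.4, rounded up to 326.

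The figure reproduces. The primary definition already has the organism rule, so restoring it for endpoint b changes nothing here. The documents give no expected rate or power for endpoint b.

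**4. Illustration with equal mixed growth in both arms.** Assumptions, none of them from the documents: true rates of 5% (standard) and 10% (short), and a share m of children without a true event counted as events. The 326 per arm is borrowed from the primary endpoint; endpoint b uses the per-protocol population, so its denominator may be smaller.

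Observed rate: p′ = p + (1 − p)m. Observed difference: (1 − m) × true difference. Power is for a two-sided 5% chi-square comparison; in the table's cases, using the unpooled confidence limit changes it by at most 0.3 points.

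| m | Standard | Short | Difference (points) | Ratio | Power |
|---|---|---|---|---|---|
| 0 | 5.00% | 10.00% | 5.00 | 2.00 | 67.9% |
| 1% | 5.95% | 10.90% | 4.95 | 1.83 | 62.4% |
| 2% | 6.90% | 11.80% | 4.90 | 1.71 | 57.5% |
| 5% | 9.75% | 14.50% | 4.75 | 1.49 | 45.9% |
| 10% | 14.50% | 19.00% | 4.50 | 1.31 | 33.6% |

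The difference itself barely moves. Power falls mainly because the background rate, and with it the variance, rises.

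**5. Illustration with unequal mixed growth.** Same formula, 326 per arm.

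- True rates equal at 5%, mixed growth 2% (standard) and 5% (short): 0.05 + 0.95×0.02 = 6.90% and 0.05 + 0.95×0.05 = 9.75%. This is a false difference of 2.85 points, significant with probability 26%.
- True rates 5% and 10%, same mixed growth: 6.90% and 0.10 + 0.90×0.05 = 14.50%. The difference widens to 7.6 points and power rises to 88%.
- True rates 5% and 10%, mixed growth reversed (5% standard, 2% short): 9.75% and 0.10 + 0.90×0.02 = 11.80%. The difference shrinks to 2.05 points and power drops to 13%.

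The sign of the effect therefore depends on a quantity that the documents do not give.

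**The case against.** The best case for the plan is that the SAP wording may be shorthand. The protocol also speaks of a positive culture without repeating the organism rule, for example in section 8.3 and in the column heads of Table 2. Protocol section 9.1 reserves the diagnosis of asymptomatic bacteriuria for listed clinicians, who would work from the protocol definition. The SAP never says that mixed growth is positive, and it keeps colony-count thresholds. This stands to the extent that one can say only that such cultures could count, not that they would. It does not remove the contradiction, because the SAP states the rule where it wants it for treatment failure and omits it here.

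Three stronger readings are tempting and are not supported.

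- A reader might infer that endpoint e has lost the same criterion. The protocol gives endpoint e no organism rule, so nothing was dropped there. It is a gap in both documents.
- A reader might infer that the omission dilutes a real difference and so favours the short course. That needs mixed growth to be similar in both arms. One arm takes active antibiotic to Day 10 and urine is collected on Days 11 to 14, so this cannot be taken for granted.
- A reader might infer that the different laboratory reporting limits bias the treatment comparison. Randomisation is stratified within site (protocol section 6.4.1, SAP section 2.4.2), so site differences should fall on both arms alike.

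**Conclusion.** Wrong as written: the protocol and the SAP contradict each other on the event rule for secondary endpoint b. Read literally, the SAP could count a multi-organism culture at threshold that the protocol does not count. The consequence is real because a null result on this endpoint is to be read as non-inferiority. Its size and direction cannot be determined from the documents: every event rate and mixed-growth rate in the illustration is an assumption, and changing them can shrink, widen or create a difference. The primary endpoint and the 326 per arm are untouched.

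The threshold signs also differ. For asymptomatic bacteriuria the SAP text shows 5×10⁴ with no sign and at least 10⁵; the protocol shows at least 5×10⁴ and more than 10⁵. These may be effects of reading the PDF, and the conclusion does not rest on them. The missing threshold for bag specimens is a gap in both documents, not something that the SAP dropped.

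**What to change.** Before unblinding:

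1. Add the single-uropathogen condition to the asymptomatic bacteriuria definition in SAP section 2.5, and say how a follow-up culture with a second organism is classified.
2. Check the colony-count signs in both documents against the source files and make them agree with the protocol's UTI definition (at least 5×10⁴ for catheter or suprapubic specimens, at least 10⁵ for clean void).
3. As separate gaps, state what counts as a positive culture for endpoint e and which threshold applies to bag specimens. A tabulation by collection method would show how far the result depends on the latter.

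The cost is a few lines of SAP text and possibly slightly fewer events for endpoint b. No sample-size figure changes.

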2.6 Clinical evaluations

Subjects will be seen by a clinician for three study visits:

1. Enrollment visit (Day 2-6)
2. Test of Cure visit (Day 11-14)
3. Outcome assessment visit (Day 24-30)

Subjects enrolled prior to Day 5 of their prescribed medication will be verified as afebrile and with no worsening of conditions on Day 5 or prior to receiving the first dose of SCOUT therapy on Day 6. In addition, subjects will be contacted by phone at the end of the study period on the Follow-up Phone Call (Day 38 - 44). Clinical evaluations at each visit will be as follows:

Day 2-6 (any time after initiation of antibiotic treatment but prior to starting the sixth day of study treatment):

To confirm eligibility including clinical improvement (afebrile and asymptomatic) a pain assessment will be performed checking for any suprapubic, abdominal, or flank pain or tenderness. If a study RN receives a report of a UTI symptom at a study visit, he/she will inform the parent/guardian that the child should be seen by a clinician licensed to diagnose and treat the UTI. If this occurs at the enrollment visit, the child will be excluded from the study and will be referred back to the PCP who initially treated the child.

Confirmation is obtained by study staff that the subject remains afebrile with no worsening of symptoms on Day 5-6 (prior to taking the first dose of SCOUT therapy on Day 6) for subjects enrolled prior to Day 5. Any volunteer that develops a fever or worsening of symptoms will be withdrawn from the study and considered an entry failure.

Day 11 -14 Test of Cure Post Treatment Visit (one – four days after completing the study product):

The child will be clinically assessed for the presence of UTI symptoms and a urine specimen will be collected for test of cure. If a study RN receives a report of a UTI

symptom at the Test of Cure visit, he/she will inform the parent/guardian that the child should be seen by a clinician licensed to diagnose and treat the UTI. The RN will document the symptom on the appropriate case report form and will contact a study physician to arrange follow-up visit.

Day 24 - 30 Outcome Assessment Visit (14-20 days following study product completion):

The child will be clinically assessed for the presence of UTI symptoms. If a urine specimen could not be collected at the Day 11 – 14 TOC Visit for asymptomatic subjects, another attempt to collect a urine sample at this visit will be made. If a study RN receives a report of a UTI symptom at the Outcome Assessment visit, he/she will inform the parent/guardian that the child should be seen by a clinician licensed to diagnose and treat the UTI. The RN will document the symptom on the appropriate case report form and will contact a study physician to arrange follow-up visit.

Day 38 - 44 Follow-up Phone Call (28-34 days after completing the study product):

Subjects will be asked regarding presence or absence of UTI symptoms, if they sought medical care for possible recurrence of UTI, and to report any inter-current illnesses.

3. Statistical Considerations

3.1 Statistical design

This is a prospective, stratified, randomized, double-blind, placebo-controlled non-inferiority clinical trial with standard-of-care antimicrobial therapy as arm 1 and short-course antimicrobial therapy placebo-controlled as arm 2.

Primary objective

To determine if halting antimicrobial therapy in children who have exhibited clinical improvement 5 days after starting antibiotic therapy (short course therapy) have the same failure rate (symptomatic UTI) through TOC (visit Day 11-14) as subjects who continue to take antibiotics for an additional 5 days (standard course therapy).

Secondary objectives

- a. To determine if short-course therapy compared to standard course therapy results in similar numbers of children experiencing a recurrent infection (relapse and reinfection) at any time after the TOC visit (Day 11-14).
- b. To determine if short-course therapy compared to standard course therapy results in similar numbers of children with asymptomatic bacteriuria at the TOC visit.
- c. To determine if short-course therapy compared to standard course therapy results in similar numbers of children that become colonized with antimicrobial resistant *Escherichia coli* (*E. coli*) and *Klebsiella pneumoniae* (*K. pneumoniae*) in the gastrointestinal tract assessed through outcome assessment visit (Day 24-30).
- d. To determine if short-course therapy compared to standard course therapy results in similar numbers of subjects presenting with clinical symptoms that may be related to UTI prior to or at the TOC visit.
- e. To determine if short-course therapy compared to standard course therapy results in similar numbers of children with positive urine cultures prior to or at the TOC visit.

Sub-study objectives

- To determine if *E. coli* and *K. pneumoniae* recovered from 2 or 3 stool cultures are more likely to be members of disease-associated subgroups within their respective species (*E. coli* phylogroups B2 and D, *K. pneumoniae* clusterKpI)

- To determine if treatment-susceptible strains recovered from cultures during treatment (culture #1 for 5-day arm; cultures #1 or #2, 10-day arm) are more likely to be members of disease-associated subgroups;
- To determine if treatment-resistant strains of either species are more likely than treatment susceptible strains to be recovered from cultures during treatment.
- To determine the overall prevalence of colonization with carbapenem-resistant Enterobacteriaceae (overall and for specific pathogens) in ambulatory children after completion of treatment for UTI.
- To compare the overall biodiversity of the gut microbial community, as measured by culture-independent marker gene sequencing at each follow-up visit following short-course and standard-course antibiotic exposure.
- To compare the overall fraction of gut microbiome community represented by gammaproteobacteria measured by culture-independent marker gene sequencing at each follow-up visit following short-course and standard-course antibiotic exposure.
- To compare the average ecological similarity between microbial communities within and between treatment groups at each follow-up following short-course and standard-course antibiotic exposure.
- To describe the breadth of bacteria present in the stool of children receiving therapy for a urinary tract infection. These data will allow for comparison of aerobic bacteria stool composition in these children and present an opportunity to contrast them to similar data available from other pediatric patient populations.

